1.2.3 Planned analyses, figures, tables

This list does not indicate which figures or tables will be included in the main document.

Figure: Flowchart of patients

Table: Patient and tumor characteristics at inclusion for patients with initial policy conservative (including patients that were operated immediately). *The list of variables to be described can be augmented with other relevant variables according to clinicians, and these will be added irrespective of the results.*

	All patients	Patients with newly detected masses	Patients with masses already in follow-up
Age			
Menopausal status			
Time in follow-up before inclusion		NA	
Tumor type			
Lesion size			
Solid parts			
...			
Presumed diagnosis (endometrioma etc)			
...			
Subjective assessment (certainty)			
Immediately operated			
Patients with a newly detected masses, n (%)		NA	NA
Symptomatic at first scan			
Pain			
Abnormal bleeding			
Other symptoms			
Outcome events			
Cyst spontaneously resolved			
Surgery performed			
Invasive tumor			
Borderline tumor			
Cyst torsion			
Cyst rupture			
Complications detected at surgery*			
No complication detected at surgery			
Patient died			

Table: List of centers, with number of patients per center. This table will include all centers (all the ones included in the sensitivity analysis). Order by total number of patients (conservative and surgery). This table is intended to be included in the appendix or supplementary material.

Center	N	Initial policy surgery	Initial policy conservative	% No info	% Useful info
Malmo, Sweden					
Leuven, Belgium					
Rome, Italy					
...					
All oncology centers					
All non-oncology centers					
All centers					

Useful information: study outcome observed, or follow-up of at least 10 months.

Table: List of centers, with number of patients per center. This table will include centers with sufficient data quality (all the ones included in the primary analysis). Order by total number of patients (conservative). This table is intended to be included in the main report.

Center	Initial policy conservative	% Useful info
Malmo, Sweden		
Leuven, Belgium		
Rome, Italy		
...		
All oncology centers		
All non-oncology centers		
All centers		

Figure: Histogram of time of follow-up before recruitment in IOTA5 for patients with a mass already in follow-up at inclusion ('old' patients)

Figure: Histogram of time of follow up scans (all follow up scans, i.e. not only the last scan per patient). This will be done once based on data from all patients, and once based on data from patients with newly detected masses only.

Figure: Cumulative incidence curve for study outcome (died, resolution, surgery). This will be done once based on data from all patients, and once based on data from patients with newly detected masses only.

Figure: Cumulative incidence curves for reason for surgery (study outcome surgery is subdivided into different reasons as specified above in Box 1; only curves for these reasons are given, not for other study outcomes (died/resolved)). This will be done once based on data from all patients, and once based on data from patients with newly detected masses only.

Figure: Cumulative incidence curves for surgery outcome (study outcome is again subdivided, but now in terms of findings at surgery as specified above in Box 1). Panel A gives all events with y-axis from 0 to 1; Panel B given zoomed in plot focusing only on malignancy, torsion, rupture. This will be done once based on data from all patients, and once based on data from patients with newly detected masses only.

Table: Cumulative incidence of study outcomes, reasons for surgery, and findings at surgery at 12 and 24 months with 95% CI; Table containing the following statistics at time points 12 months and 24 months: cumulative incidence with standard error and 95% CI. This will be done once based on data from all patients, and once based on data from patients with newly detected masses only.

	12 months	24 months
Study outcome		
Cyst resolution		
Patient died		
Surgery performed		
Reason for surgery		
Suspicion of malignancy		
Pain ^b		
Patient request/opportunistic ^c		
Findings at surgery		
Invasive		
Borderline		
Torsion		
Cyst rupture		
Minor complications		
No complications		

Table: Table of all cases with confirmed malignancy, rupture, or torsion, with descriptive information. *The exact list of parameters to be described should still be defined.*

Case	New or known mass at inclusion	Time in follow up before surgery	Finding(s) at surgery	Age at inclusion	Lesion size at first scan	Change in lesion size	...
1							
2							
3							
4							
5							
6							
7							
...							

Table: Cumulative incidence of each outcome (death (any cause), spontaneous resolution, surgery (any reason), malignancy, torsion, rupture at 24 months with 95% CI for all levels of all subgroup variables for patients with new masses. This will be done based on data from patients with newly detected masses only.

Subgroup variable	Death (any cause)	Spontaneous resolution	Surgery (any reason)	Malignancy	Torsion	Rupture
Tumor type						
Unilocular						
Unilocular-solid						
...						
Presumed diagnosis						
Endometriosis						
...						
Subjective assessment						
Certainly benign						
Probably benign						
...						
Lesion size						
median split (4 cm?)						
cut-offs 3, 4, 5, 7, 10 cm						
...						
Menopausal status						
Premenopausal						
Postmenopausal						

Table: For cases with initial policy conservative but who were nevertheless immediately operated: overview of histology at surgery. This will be done based on data from patients with newly detected masses only.

Histology	N (%)
Endometrioma	
Dermoid	
...	
Borderline	
...	

Table: Overview of reasons for surgery for cases with initial policy conservative, stratified by whether they were nevertheless immediately operated or not. This will be done based on data from patients with newly detected masses only.

Reason for surgery	Immediately operated N (%)	Patients with FU N (%)
Suspicion of malignancy		
Pain		
Suspected torsion		
Suspected cyst rupture		
Acute pain		
Chronic pain		
Patient request / opportunistic		
Fertility concerns		
Patient request, other		
Opportunistic		

Table. Sensitivity analysis using data from all centres. This will be done based on data from patients with newly detected masses only.

	12 months	24 months
Study outcome		
Cyst resolution		
Patient died		
Surgery performed		
Reason for surgery		
Suspicion of malignancy		
Pain ^b		
Patient request/opportunistic ^c		
Findings at surgery		
Invasive		
Borderline		
Torsion		
Cyst rupture		
Minor complications		
No complications		

Table. Sensitivity analysis including patients that were immediately operated. This will be done based on data from patients with newly detected masses only.

	12 months	24 months
Study outcome		
Cyst resolution		
Patient died		
Surgery performed		
Reason for surgery		
Suspicion of malignancy		
Pain ^b		
Patient request/opportunistic ^c		
Findings at surgery		
Invasive		
Borderline		
Torsion		
Cyst rupture		
Minor complications		
No complications		

IOTA5 interim analysis

1.1 Objective

To assess the performance of prediction models and subjective assessment for ovarian tumor diagnosis when evaluated on all patients presenting with an adnexal mass: patients operated after the recruitment scan (without having received conservative follow-up) and patients managed conservatively with ultrasound follow-up. Because this is not the same population as the population on which the models were developed (masses when selected for surgery), this is not a true validation study.

1.2 Population

Adult patients with an adnexal mass, who are included in the IOTA5 interim dataset (cf inclusion and exclusion criteria), except masses that are deemed clearly physiological if less than 3cm in maximal diameter. The interim dataset contains patients recruited in the IOTA5 study between 1 January 2012 and 1 March 2015, with follow-up data up to 30 June 2017.

1.3 Data

The IOTA5 database will be used for the analysis and the following in- and exclusion criteria will be used.

Inclusion criteria:

- Recruitment scan between 1 January 2012 and 1 March 2015.
- Patients who were not already in follow-up at a center before the recruitment scan ('new' patients) (i.e. new patients)
- Patients recruited in centers AGR (Athens), CIT (Milan), FLI (Florence), GBE (Genk), IUK (London), LBE (Leuven), MIT (Milan), MPO (Katowice), MSW (Malmö), NCI (Milan), NUK (Nottingham), OIT (Monza), PSP (Pamplona), RIT (Rome), SIT (Cagliari), SSW (Stockholm), TIT (Trieste). i.e. centers with 'good' follow-up data and surgery data. The are the 'main centers'.

- Other centers (BIT, PCR, LPO, CAI, CEG, CRI, DEP, UDI, BAI, BCH, FIT, KPO, LIP, MCA, MFR, PFR, RZT, TUS, VAS) will be included in a supplementary analysis of performance in masses that are operated without follow-up (within 120 days after inclusion), together with the main centers. See below.

Exclusion criteria:

- Patients who did not give consent; data from patients who withdrew consent during the study will not be used either
- Younger than 18 years at first scan
- Patients who were already in follow-up at a center before the recruitment scan ('new' patients) (i.e. old patients)
- Cysts that are deemed clearly physiological if less than 3 cm in maximum diameter are not eligible for inclusion.

Multiple masses:

When the examiner detected multiple masses, the mass with the most complex ultrasound morphology was defined as the dominant mass. If multiple masses had similar morphology, the largest mass or the one best accessible with ultrasound was denoted as dominant.

Outcome:

Some patients received surgery without follow-up, some received follow-up only, some received follow-up with surgery later on, and for some patients we did not know what happened after the inclusion visit. We determine the dichotomous outcome (benign or malignant tumor) using the following rules:

- A. If surgery, irrespective whether there was FU or not:
 - If the resulting histology was benign: classify as *benign (B1)*
 - If the resulting histology was malignant:
 - o If surgery was within 120 days from the inclusion visit: classify as *malignant at inclusion (M1)*
 - o If surgery was >120 days after the inclusion visit, but subjective assessment was probably or certainly malignant (including borderline) at every visit: classify as *malignant at inclusion (M2)*
 - o If surgery was >120 days after the inclusion visit, but subjective assessment was not always probably or certainly malignant (including borderline) at every visit: classify as *uncertain (U1)*

- B. The tumor spontaneously resolved at any point during follow-up: classify as *benign*

- C. The patient did not receive surgery, the tumor did not resolve, and the last follow-up visit was ≥ 10 months after the inclusion visit:

- If subjective assessment was consistently labeled as probably or certainly benign during the first 14 months of follow-up (specific definition: subjective assessment was benign at the earliest visit after ≥ 10 months of follow-up, and subjective assessment was benign at all visits up to 14 months of follow-up): classify as *benign (B2)*
- If subjective assessment was consistently labeled as probably or certainly malignant (including borderline) during first 14 months of follow-up (specific definition: subjective assessment was borderline/malignant at the earliest visit after ≥ 10 months of follow-up, and subjective assessment was borderline/malignant at all visits up to 14 months of follow-up): classify as *malignant (M3)*
- Else, subjective assessment was inconsistent/uncertain during the first 14 months of follow-up: classify as *uncertain (U2)*

D. Other cases: classify as *uncertain*

- Patients that received follow-up of less than 10 months, without receiving surgery or experiencing spontaneous resolution of the tumor. Reasons for such short follow-up can be death, withdrawal from the study, or being lost to follow-up. (U3)
- Patients for which we did not have information after the inclusion visit. Reasons for such short follow-up can be death, withdrawal from the study, or being lost to follow-up. (U4)

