Multiple imputation will be performed to deal with missing values for CA125 and outcome. Imputations will be created using the method of fully conditional specification with the mice package in R. We will generate 100 imputations, leading to 100 completed datasets. To estimate the missing values for CA125, we will use predictive mean matching regression using the outcome, variables that are probably related to either the level of CA125 itself, or to the unavailability of CA125 (i.e. a binary indicator indicating for each patient whether CA125 was missing). As the distribution of serum CA125 was heavily skewed, the log-log transformation of CA125 will be used (i.e., $\log(\log(\text{CA125} + 1))$). In the imputation model, the following variables will be used: Presumed endometrioma, level of certainty at subjective assessment at inclusion (6 groups: certainly benign, probably benign, benign but uncertain, malignant but uncertain, probably malignant, certainly malignant), patient age, type of center (oncological versus non-oncological center), lesion largest diameter, proportion of solid tissue (maximum diameter solid component divided by maximum diameter of lesion), number of locules (1, 2-10, >10, other), number of papillations, presence of shadows, presence of ascites, presence of metastases, bilaterality, pelvic pain, personal history of ovarian cancer, papillary height, papillary flow, color score, echogenicity of cyst fluid, and outcome (benign, borderline, stage I primary invasive, stage II-IV primary invasive, secondary metastatic). Descriptive characteristics of the tumor were based on the inclusion scan. Uncertain outcomes (cf above) will be considered missing, and hence the outcome will be imputed).

Note that some patients are classified as having a malignant tumor based on clinical and ultrasound information during follow-up (cf category M3 above). For these patients, we do not have a classification into one of the malignancy subtypes. The multiple imputation procedure will therefore treat the outcome as missing such that it will be imputed. The imputed outcomes will be evaluated, and the most commonly imputed malignant type will be used as the outcome in the analysis.

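### SAP 1.3, rule C, states the B2 and M3 outcome criteria twice, once with a certainty condition and once without, so non-operated masses rated benign or malignant 'but uncertain' have no settled class

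*SAP*

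**What the plan says.** Rule C has three branches.

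- **B2 (benign).** The lead clause reads "If subjective assessment was consistently labeled as probably or certainly benign during the first 14 months of follow-up". The specific definition in brackets then requires that "subjective assessment was benign at the earliest visit after ≥ 10 months of follow-up" and that "subjective assessment was benign at all visits up to 14 months of follow-up".
- **M3 (malignant).** The lead clause reads "If subjective assessment was consistently labeled as probably or certainly malignant (including borderline) during first 14 months of follow-up". Its specific definition makes the same change, ending with "subjective assessment was borderline/malignant at all visits up to 14 months of follow-up".
- **U2 (uncertain).** This is the remainder: "Else, subjective assessment was inconsistent/uncertain during the first 14 months of follow-up".

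SAP 1.5.1 lists six levels of subjective assessment. The middle two are "benign but uncertain, malignant but uncertain", called the two unsure levels below. Under SAP 1.5.1 and 1.5.2, U-class outcomes are treated as missing and multiply imputed in the primary analysis. B2 stays benign. M3 stays malignant, with only the tumour subtype taken from the imputation.

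**The concern.** Each class has two tests, and they are not equivalent. The lead clauses ask for a label and a degree of certainty; the specific definitions ask for the label alone. A woman rated benign with uncertainty at 3, 6 and 12 months, without surgery or resolution, is U2 under one half of the rule and B2 under the other. Her malignant-rated counterpart is U2 or M3.

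At stake is the reference standard of the primary analysis. If the label-only half is coded, masses about which the examiner is unsure are given a definite outcome without histology. A model that assigns high risk to such a mass is then charged with a false positive when the label is benign, and a model that assigns low risk is charged with a false negative when the label is malignant, although the true state is unknown. Subjective assessment is itself one of the tests being evaluated, as a binary label (SAP 1.4). The label-only half therefore extends the overlap between test and reference to the ratings in which the examiner had least confidence. Exposure is greatest in the subgroup with at least one follow-up scan (SAP 1.5.7), because rule C applies there. That section already foresees that malignancies per centre may be too few for meta-analysis.

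**Working it through.** The documents give no count or sample-size figure for this point, so there is nothing to reproduce. The check compares the wording and then enumerates ratings.

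**1. Are label and certainty separate items?** Yes.
- Protocol, Subjective assessment: item A is the label (benign, borderline or malignant). Item B is a five-level certainty score whose third level means uncertain.
- SAP of 27 December 2017, section 1.1: the inclusion criterion names the benign label and, joined to it, a certainty of certainly or probably benign.
- SAP 1.4: subjective assessment without a qualifier is a binary judgement.
- SAP 1.5.1: the two unsure levels are distinct from the 'probably' and 'certainly' levels.

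**2. The two halves of rule C, same rating at every qualifying visit**

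| Rating | Lead clause | Specific definition, read literally |
|---|---|---|
| Certainly or probably benign | B2 | B2 |
| Benign, unsure | U2 | B2 |
| Malignant, unsure | U2 | M3 |
| Probably or certainly malignant | M3 | M3 |

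Four of the six levels agree and two do not.

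**3. Mixed ratings over several visits.** With k visits, the patterns carrying a benign label throughout number 3^k. Those that also avoid the unsure level number 2^k. The halves disagree on the difference, and the same count applies on the malignant side.
- k = 3 (3, 6 and 12 months): 27 − 8 = 19 on each side, so 38 of 6^3 = 216 patterns.
- k = 4 (adding the inclusion scan): 81 − 16 = 65 on each side, so 130 of 6^4 = 1,296 patterns.

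Every disagreeing pattern contains at least one unsure rating. None is B2 under one half and M3 under the other. These are counts of patterns, not proportions of women.

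**4. Comparison with rule A.** When surgery takes place more than 120 days after inclusion and histology is malignant, M2 requires a probably or certainly malignant assessment at every visit; otherwise the case is U1. An unsure malignant rating thus makes the outcome uncertain even with malignant histology. Under rule C's label-only half, the same rating with no histology is fixed as malignant.

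**5. Analyses affected**
- Primary analysis (SAP 1.5.2): affected, because B2 and M3 are fixed and U2 is imputed.
- Analysis excluding U1 to U4 (SAP 1.5.8): affected, because its sample depends on the same split.
- Analysis imputing B2, M2, M3 and U1 to U4 (SAP 1.5.2 and 1.5.8; the latter prints N2, apparently for M2): not affected by this boundary, because every unresolved rule C class is imputed.

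**6. Illustration of size, on assumed rates.** Let q be the chance per visit that an always-benign-labelled mass is rated unsure. With independent visits, the share switching between B2 and U2 is 1 − (1 − q)^k. If the same women are unsure at every visit, the share is simply q.

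| Assumed q | Same women every visit | Independent, k = 3 | Independent, k = 4 |
|---|---|---|---|
| 1% | 1% | 3.0% | 3.9% |
| 3% | 3% | 8.7% | 11.5% |
| 5% | 5% | 14.3% | 18.5% |
| 10% | 10% | 27.1% | 34.4% |

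The documents give no value for q, so the table shows sensitivity to an assumption and does not estimate the effect.

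**The case against.** **The bracketed text may be shorthand.** Section 1.3 attaches a degree of certainty in M2, in U1 and in both rule C lead clauses. The brackets may only spell out which visits count, with the bare label standing for the phrase just used. The U2 wording favours this. The reading is plausible and is probably what was meant. It does not remove the problem: U2 is an 'else' class, reached only after B2 and M3 have been tried, so it cannot take back a case that a literally coded specific definition has already assigned.

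**Label-only may be closer to the protocol.** The Protocol (Objectives; Statistical analysis) calls a non-operated mass benign if there are no malignant ultrasound features, or no clinical cancer diagnosis, at one year. Neither statement requires a certainty level. This stands as an argument about B2, but it does not reconcile the SAP with itself. If label-only was intended, the lead clauses and U2 would have to change instead.

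**Few women may be affected.** The Protocol (Definition of benign ultrasound morphology) reserves conservative management for masses the examiner is sure or nearly sure are benign, and operated and resolved masses leave rule C. This stands and limits the likely size. However, the 2019 analysis has no certainty criterion at entry, and ratings can change between visits.

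**Stronger readings that the documents do not support.**
- A reader might infer a second conflict, on timing, when no scan falls between 10 and 14 months. The specific definition settles this: the earliest visit at or after 10 months governs. There it adds detail that the lead clause lacks; on certainty it drops a condition that the lead clause states.
- A reader might try to state how many malignancies would be fixed as benign. The documents give neither the number of rule C women nor the malignancy rate among unsure ratings.
- A reader might equate these masses with the uncertain tumours that the Protocol's IOTA phase 2 summary says need a second-stage test. That remark comes from a model-validation study. It does not concern non-operated masses still labelled benign at one year.

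**Conclusion.** The point holds as a defect in the definition of the primary reference outcome. Rule C gives two non-equivalent tests for B2 and for M3, and they part exactly at the two unsure levels. The consequence is limited: cases move between fixed and imputed, never between benign and malignant. One planned sensitivity analysis is immune to the split, so the plan already tests, in part, its reliance on outcomes set by subjective assessment.

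The size is unknown and may be small. The conclusion rests on the text of rule C and on the documents' separation of label from certainty, not on the illustrative rates. It should be corrected because it concerns a stated rule of the primary analysis and the correction is cheap.

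**What to change.** Repeat the certainty condition inside the specific definitions, so that they agree with the lead clauses, with U2 and with rule A.

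- **B2:** benign label with certainty 'probably' or 'certainly' at the earliest visit at or after 10 months and at all visits up to 14 months.
- **M3:** the same visits, with a borderline or malignant label and certainty 'probably' or 'certainly'.
- **U2:** every other combination, stating explicitly that an unsure rating of either kind at any of those visits leads here.

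Check which version the outcome-derivation code implements, and report how many women change class, separately for B2 to U2 and M3 to U2. No change to the visit timing is needed.

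The cost is a few words in the SAP, one condition in the derivation code, and slightly more imputed outcomes.
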